4.1. Primary Objective

To investigate the effect of LY3209590 compared with insulin degludec in HbA1c change from baseline to Week 26 among the study participants with Type 1 diabetes mellitus (T1DM).

4.2. Secondary Objectives

4.2.1. Efficacy

To investigate the efficacy of LY3209590 compared with insulin degludec for the following endpoints:

1. HbA1c change from baseline to Week 12
2. Fasting glucose change from baseline to Weeks 12 and 26
3. Prandial insulin dose change from baseline to Week 12 and 26

4.2.2. Safety

To investigate the safety of LY3209590 compared with insulin degludec for the following endpoints:

1. Incidence and rate of hypoglycemia events during the treatment period
2. Incidence of treatment-emergent serious adverse events (TE-SAEs)

4.3. Exploratory Objectives

To investigate other safety and efficacy measures for LY3209590 for the following endpoints:

1. Insulin dose at baseline and Week 26;
2. Treatment-emergent adverse events (TEAEs);
3. Incidence and rate of hypoglycemia events during the post-treatment follow-up period;
4. Discontinuation of investigational product (IP) due to adverse events (AEs);
5. Clinical laboratory results;
6. Injection site reactions;
7. Insulin dose for prandial and basal insulin during treatment period and follow-up period
8. Liver aminotransferase change from baseline to Weeks 12 and 26;
9. Triglyceride and FFA change from baseline to Weeks 12 and 26;
10. Body weight change from baseline at Weeks 12 and 26;
11. Glucose time in target range, time in hyperglycemia, time in hypoglycemia using CGM

12. Lipids (cholesterol, LDL, HDL, triglycerides)
13. Six-point self-monitoring of blood glucose (SMBG) profiles
14. The frequency of antibody formation to LY3209590;
15. Incidence and percentage of missed doses of LY3209590 and insulin degludec.

5. A Priori Statistical Methods

5.1. General Considerations

All data will be entered, verified, and archived at a contract research organization (CRO) external to Eli Lilly and Company (Lilly) and/or at Lilly. Data listings, summaries, and analyses will be performed by a CRO and/or by Lilly under the guidance and approval of statisticians at Lilly.

Statistical analysis of this study will be the responsibility of sponsor or its designee. Any change to the data analysis methods described in the protocol will require an amendment only if it changes a principal feature of the protocol. Any other change to the data analysis methods described in the protocol, and the justification for making the change, will be described in this SAP and/or the clinical study report(CSR). Additional exploratory analyses of the data will be conducted as deemed appropriate.

The following populations are defined for purpose of analysis:

Population	Description
Entered/Enrolled Population	All participants who sign the ICF
Randomized Population	All participants assigned to treatment, regardless of whether they take any doses of study treatment, or if they took the correct treatment. The participants previously randomized to LY3209590 Algorithm 2 will be pooled with the participants randomized to Algorithm 1 and all of these participants will be analyzed as one treatment group of LY3209590.
Efficacy Population	All participants randomized to either LY3209590 Algorithm 1 or insulin degludec and took at least 1 dose of study treatment. Participants will be analyzed according to the treatment they were assigned.
Safety Population	All participants randomly assigned to study intervention and who took at least 1 dose of study treatment. The participants previously randomized to LY3209590 Algorithm 2 will be pooled with the participants randomized to Algorithm 1 and all of these participants will be analyzed as one treatment group of LY3209590.
Pharmacokinetic Population	All randomized participants who received at least 1 dose of LY3209590 and have at least 1 evaluable PK sample.

Abbreviations: ICF = informed consent form; PK = pharmacokinetics.

Unless otherwise stated, the efficacy analyses will be conducted on efficacy analyses set (EAS) based on the Efficacy Population using the data up to the study treatment discontinuation

(defined as the observed data with collection date before or on the last dose date +10 days). Sensitivity analyses for selected efficacy measures may be conducted on the Randomized Population using the data up to the study treatment discontinuation.

Unless otherwise stated, the safety analyses will be conducted on the safety analyses set based on the Safety Population using all data collected during the study including treatment and follow-up period regardless of the treatment disposition status. The safety measures will be summarized and compared between LY3209590 (by pooling LY3209590 Algorithm 1 and LY3209590 Algorithm 2 data) and insulin degludec. Safety parameters derived from CGM measures will be summarized and compared between LY3209590 Algorithm 1 and degludec.

Unless otherwise specified, the baseline value used for the analyses will be the last non-missing value obtained for each participant prior to or on the date of first study IP dose (or randomization visit date if first dose date is missing). The baseline liver enzyme lab measures will be the average of all assessments prior to and at randomization visit.

All tests of treatment effects will be conducted at a 2-sided alpha level of 0.1, unless otherwise stated, and all confidence intervals (CIs) will be given at a 2-sided 90% level.

Puerto Rico and the United States (US) are always pooled in the analysis, as Puerto Rico will be considered part of US during randomization. All analyses using country in the model will use pooled country, unless otherwise specified. No other pooling of countries is needed.

For continuous measurements, summary statistics will include sample size, mean, median, standard deviation (SD), minimum, and maximum. For certain variables that are considered to be log-normally distributed, the geometric mean and coefficient of variation (CV) will be provided instead.

For categorical measurements, summary statistics will include sample size, frequency, and percentage. Fisher's exact test will be used. Chi-squared test will be used for multi-category variables.

A mixed-model repeated measures (MMRM) model will be used for continuous outcomes with repeated postbaseline measurements to compare treatment arms, unless otherwise noted.

Treatment comparisons will be performed by the treatment difference in least-squares means (LS mean). Means and LS mean by treatment group and visit, along with the standard error of LS mean, 90% CIs of the treatment differences along with the p-value for the treatment comparison will be displayed. For the change from baseline, p-value for the within-treatment comparison will also be displayed. For selected parameters, log-transformed values will be analyzed in the MMRM model instead. The actual, change from baseline and percentage change from baseline will be presented using the derivation based on the output from the MMRM model.

In this study, the negative binomial regression will estimate Group Mean instead of LS mean and use delta method to estimate the standard error of the Group Mean (Qu and Luo 2015). Group Mean is defined as the mean response in the treatment group for the studied population. The difference between LS mean and the Group Mean is that LS mean estimates the response by

taking the inverse link function on mean covariates, while the Group Mean takes the inverse link function on individual patient covariates first and then averages over all patients.

Sensitivity analyses may be conducted for selected safety and efficacy measures by excluding data from patients who significantly deviated from the study dose algorithm, for example patients who received repeated loading doses. The study team will review patient study dose data and identify the patients who will be excluded from the sensitivity analyses prior to the final lock of the study data.

All analyses will be implemented using SAS Enterprise Guide Version 7.1 or above.

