6.1.1. Selection and Timing of Doses

For patients randomly assigned to LY3209590, a loading dose will be determined using Table 1 in Algorithm 1 (see Section 10.8). The weekly dose adjustment thereafter will be based on guidance provided in Section 10.8. The doses will be administered at approximately the same time and day each week. The actual date, time and dose of each dose administrations (LY3209590 and insulin degludec) will be recorded in the participant's diary (and participant's medical record when administered at the site).

If a patient misses a scheduled dose of LY3209590, it should be administered as soon as possible, but no later than 3 days after the scheduled administration. If more than 3 days have elapsed since the scheduled administration, the dose should be skipped and the next injection will occur at the next scheduled day and time.

Insulin degludec should be administered at the same time each day adjusted per the modified Riddle algorithm (Section 10.8).

Patients who miss a dose of insulin degludec should inject their daily dose during waking hours upon discovering the missed dose. Instruct patients to ensure that at least 8 hours have elapsed between consecutive insulin degludec injections (Tresiba® USPI).

For details on the titration algorithms to be used, refer to Section 10.8.

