6.7.1. Treatment after Study Completion

The last study treatment administration for patients treated with LY3209590 will be at Week 25 and for patients treated with insulin degludec the evening before the last study visit at Week 26. The washout of LY3209590 may take up to 10 weeks to complete. Any appropriate basal insulin treatment must therefore be instituted slowly and under regular supervision of BG profiles after discontinuation of LY3209590. Since CCI [REDACTED]

[REDACTED] Therefore, a slow up-titration of another basal insulin is necessary to prevent hypoglycemia due to overlapping insulin action. For example, no insulin would be required until the study participant's FG increases to >100 mg/dL, and then daily basal insulin would be initiated and adjusted based on FG.

Study participants assigned to the insulin degludec treatment group will switch to the basal insulin used before entering the study. If insulin degludec was the pre-study basal insulin, they can continue with the same dose used until Visit 20 of the study. If they switch to another basal insulin (e.g., insulin glargine), study participants should inject a daily dose, which is 20% lower than the last dose of insulin degludec used before Visit 20 and titrate under supervision of the investigator using the country-specific label for their pre-study basal insulin.

7. Discontinuation of Study Intervention and Participant Discontinuation/Withdrawal

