7.1.2. Temporary Discontinuation

In certain situations after randomization, the investigator may need to temporarily discontinue (interrupt) IP (e.g., due to an AE or a clinically significant laboratory value). The maximum time allowed for a temporary interruption of IP is 14 days. If IP interruption is due to an AE, the event is to be documented and followed according to the procedures in Section 8.3 of this protocol. Investigators should inform the sponsor that IP has been temporarily interrupted. Every effort should be made by the investigator to maintain patients on IP and to restart IP after any temporary interruption, as soon as it is safe to do so. The data related to temporary interruption of IP and use of non-study insulin will be documented in source documents and entered in the eCRF.

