9.4.1. General Considerations

Unless otherwise stated, the efficacy analyses will be conducted on efficacy analyses set (EAS) based on the Efficacy Population using the data up to the study treatment discontinuation (defined as the observed data with collection date before or at the last dose date +10 days). Sensitivity analyses for selected efficacy measures may be conducted on the Randomized Population using the data up to the study treatment discontinuation.

Unless otherwise stated, the safety analyses except for hypoglycemia will be conducted on the safety analyses set based on the Safety Population using all data collected during the study including treatment and follow-up period regardless of the treatment disposition status. The details for analyses of hypoglycemia will be documented in the SAP.

Unless otherwise specified, the baseline value used for the analyses will be the last nonmissing value obtained for each participant prior to or on the date of first study IP dose (or randomization visit date if first dose date is missing). The baseline liver enzyme lab measures will be the average of all assessments prior to and at randomization visit.

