9.4.3. Primary endpoint(s)

The primary objective is to compare the HbA1c change from baseline to Week 26 between LY3209590 treatment and insulin degludec. It is intended to estimate the treatment differences in the change in HbA1c from baseline to 26 weeks if participants adhered to the treatment without intercurrent events (stop of the study medication). It is a type of hypothetical estimand based on International Council for Harmonisation (ICH) E9(R1). Only data before the occurrence of the intercurrent events (stop of the study medication) will be included in the analysis and the resulting missing values will be imputed implicitly in the mixed-effect model for repeated measurements (MMRM) analysis. The MMRM model will include treatment, country, visit, and treatment by visit interaction as fixed factors and the baseline of the dependent variable as a continuous covariate.

As a sensitivity analysis, the treatment differences in HbA1c change from baseline to Week 26, only if patients could complete the treatment, will also be estimated. More details will be specified in the SAP.

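### The last-dose-plus-10-days cut-off treats one skipped final weekly dose as discontinuation and usually drops that LY3209590 completer's Week 26 HbA1c, against the primary estimand's own definition

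*SAP*

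**What the plan says.** Protocol 9.4.1 and SAP 5.1 restrict efficacy analyses to data up to discontinuation of study treatment. The SAP wording is "defined as the observed data with collection date before or on the last dose date +10 days", and the protocol has the same rule in almost the same words. Neither document varies the rule by arm or makes an exception for a participant who missed a dose without stopping.

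The dosing schedules differ by arm (protocol 6.7.1). "The last study treatment administration for patients treated with LY3209590 will be at Week 25", and degludec ends "for patients treated with insulin degludec the evening before the last study visit at Week 26". The Schedule of Activities puts Visit 19 at Week 24 and Visit 20 at Week 26, each ± 3 days. Week 25 is therefore not a scheduled visit, and protocol 4.1.1 allows home dosing in that period. For a late weekly dose, protocol 6.1.1 says: "If more than 3 days have elapsed since the scheduled administration, the dose should be skipped".

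For the primary estimand, protocol 9.4.3 says: "Only data before the occurrence of the intercurrent events (stop of the study medication) will be included in the analysis". SAP 5.7 puts missing values down to early discontinuation of treatment. It handles them through an MMRM on Weeks 6, 12, 16 and 26, assuming missing at random. Protocol 7.1.2 treats interruption as something separate from discontinuation: "The maximum time allowed for a temporary interruption of IP is 14 days".

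**The concern.** The rule is meant to find the point at which a participant stopped treatment, but it does so by counting days since the last dose. For a weekly drug whose last planned dose comes a week before the primary assessment, one omitted injection is enough to cross the line. A participant who follows the missed-dose instruction, never stops treatment and attends Visit 20 on time is then analysed as having discontinued, and the primary value is set aside. On daily degludec, the same limit is reached only after a long run of missed doses.

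The estimand and the data rule therefore disagree about who has had the intercurrent event, and they disagree far more readily in one arm. Non-inferiority is declared on this analysis. The SAP is also inconsistent with itself. Its CGM section (5.11.1) censors only once the product has been stopped for good, and its exposure section (5.10.1) allows for the dosing interval by ending exposure at the last dose for degludec and 7 days later for LY3209590.

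**Working it through.** **Inputs.** Cut-off of 10 days (SAP 5.1, protocol 9.4.1). Nominal days: Week 24 = 168, Week 25 = 175, Week 26 = 182. Visit 20 on days 179 to 185 (Schedule of Activities). SD 1.1%, margin 0.4%, true difference 0, two-sided alpha 0.1, 95 completers per arm (protocol 9.2). The skipping rate f and the unexplained HbA1c difference d are assumptions; the documents give neither.

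**Step 1: days from last dose to Visit 20.**
- LY3209590, Week 25 dose on its day: 179 − 175 = 4 to 185 − 175 = 10. All kept. If the dose is up to 3 days late, the gap is 1 to 10 days and all are still kept.
- LY3209590, Week 25 skipped, Week 24 dose on its day: 179 − 168 = 11 to 185 − 168 = 17. Cut on every permitted visit date.
- LY3209590, Week 25 skipped, Week 24 dose anywhere within ± 3 days (days 165 to 171): 179 − 171 = 8 to 185 − 165 = 20. Of the 7 × 7 = 49 date pairs, 6 have a gap of 10 days or less (three for day 171, two for day 170, one for day 169), so 43 are cut. This counts date pairs; it is not a probability.
- Degludec, last k evening doses missed: gap = k + 1. Nine missed doses give 10 days (kept); ten give 11 (cut).

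**Step 2: the plan's own power.** Power = Φ(0.4 / (1.1 × √(1/n₁ + 1/95)) − 1.645). With n₁ = 95 this is Φ(2.506 − 1.645) = 80.5%, which agrees with the stated minimum of 80%.

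**Step 3: effect of the lost values.** Let f be the share of LY3209590 completers whose Week 26 value is cut, and d the part of their Week 26 HbA1c that the earlier visits do not predict. Then n₁ = 95 × (1 − f) if a cut participant contributes nothing, and absolute bias = f × d. If skippers do worse than predicted, one-sided type I error at the margin is Φ(f × d / SE − 1.645), with SE = 1.1 × √(1/n₁ + 1/95).

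| f (assumed) | values lost of 95 | power from lost information alone | bias at d = 0.3 | type I error at d = 0.3 |
|---|---|---|---|---|
| 1% | 0.95 | 80.4% | 0.003 | 5.2% |
| 2% | 1.9 | 80.2% | 0.006 | 5.4% |
| 5% | 4.75 | 79.6% | 0.015 | 6.0% |
| 10% | 9.5 | 78.7% | 0.030 | 7.2% |

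At d = 0 the bias is zero and type I error stays at 5.0%. If skippers do better than predicted by 0.3, the bias works against LY3209590. At f = 10%, power is then Φ((0.4 − 0.03)/0.164 − 1.645) = 73.0%.

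**Step 4: check by simulation.** Two visits with an assumed correlation of 0.7 were simulated, imputing the later visit from the earlier one. Bias was about 0 when skipping was random or depended only on the earlier HbA1c. With d = 0.3 it was −0.015 at f = 5% and −0.031 at f = 10%, which matches f × d.

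**The case against.** The strongest defence is that 10 days equals the 7-day dosing interval plus the 3-day visit window, so the rule fits the schedule and keeps everyone who takes the Week 25 dose, even late. That is true. It suggests the aim was to keep completers' Visit 20 data, and the rule misses that aim for completers who skip the dose as instructed.

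Second, the target is the effect if everyone adhered, and a value taken 11 or more days after a weekly dose is not clearly an adherent one. This has some force. But the protocol names only stopping as the event, permits interruption, and says LY3209590 washout may take up to 10 weeks (6.7.1). Nor does the rule enforce adherence evenly, since nine missed degludec doses pass.

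Third, the supportive estimand in SAP 5.7 keeps all available Week 26 data, and missed doses are summarised by arm. Both make the issue more visible. However, the supportive analysis also changes the model and the handling of missing values, so it cannot isolate this effect, and the non-inferiority decision does not rest on it.

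Three stronger readings are tempting and should be resisted:
- *The rule does bias the result, in favour of LY3209590.* Deletion makes data missing, and the MMRM copes if the values are missing at random. Skippers need not have high HbA1c. A dose may be withheld for an adverse event (protocol 7.1.2), and hypoglycemia can lead to reducing or stopping the product (6.1.2.2), so the effect could run either way.
- *Only the LY3209590 arm is affected.* A degludec interruption of more than 10 days that runs up to Visit 20 is cut too. In either arm, an interruption that ended before the final doses does not matter, because the last dose date moves forward.
- *The bias could reach a quarter of the margin.* That takes 10% skipping × a raw 1.0 point difference = 0.10 points. Neither figure is in the documents, and the product ignores what the MMRM recovers from Weeks 6, 12 and 16.

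**Conclusion.** Wrong as written. The day counts follow from the documents' own schedule: skipping only the Week 25 dose removes the primary value on every Visit 20 date when Week 24 was dosed on its nominal day, and in 43 of 49 date pairs otherwise. That conflicts with the estimand's single named intercurrent event and with the SAP's own CGM rule.

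The consequence is a possible bias, not a demonstrated one. Its size and direction depend on how many participants skip Week 25 and how far their values depart from the MMRM prediction. Over the assumed ranges (f of 1 to 10%, d of 0 to 0.3 points) the bias is 0 to 0.03 HbA1c points. The loss of information alone costs at most 1.8 points of power (80.5% − 78.7%). The effect is probably small. The case for acting is that this is an avoidable exclusion, falling unevenly on the two arms, in the analysis that decides non-inferiority.

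**What to change.** Before database lock, change the definition in SAP 5.1 and align protocol 9.4.1 as follows:
- Apply the + 10 days cut-off only to participants who permanently discontinued study treatment.
- Count as discontinued anyone with a recorded permanent stop, and also anyone whose dosing gap, measured from the first missed scheduled dose, exceeds the 14-day limit in protocol 7.1.2. This borrows the limit for the analysis only and changes nothing in patient management.
- Keep the Visit 20 HbA1c of all other treatment completers.
- Report, by arm, how many Week 26 values the rule removes.

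The 14-day ceiling is needed because relying on a recorded stop alone would admit someone who quietly stopped weeks earlier. With nominal dosing, a skipped Week 25 dose gives 179 − 175 = 4 to 185 − 175 = 10 days from the first missed dose, so the value is kept. If Weeks 23 to 25 are all missed, the gap is 179 − 161 = 18 days or more and the value is cut. Degludec is kept up to 14 consecutive missed doses.

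The cost is a short SAP revision. Dose and interruption dates are already collected (protocol 6.4 and 7.1.2). Both documents allow a change of method that is not a principal feature to be made in the SAP with a justification; if the sponsor regards this as a principal feature, the protocol must be amended. The downside is that a few values taken more than 10 days after the last dose are kept. With both Weeks 24 and 25 missed, and nominal dosing before that, the longest such gap is 182 − 161 = 21 days.

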Fasting		X	X			X		X						X		X		X	X	X	X	X	X	Minimum 8 hours	
LY3209590 and insulin degludec accountability (collect used and unused IP)																		X		X	X			X	

Abbreviations: AE = adverse event; BG = blood glucose; CGM = Continuous Glucose Monitoring; CV = cardiovascular; ECG = electrocardiogram; eCRF = electronic case report form; eGFR = estimated glomerular filtration rate; ET = early termination; FSH = follicle-stimulating hormone; HbA1c = glycated hemoglobin; HDL = high density lipoprotein; HIV = human immunodeficiency virus; IP = investigational product; IWRS = interactive web response system; LDL = low density lipoprotein; LY = LY3209590; PC = product complaint; PK = pharmacokinetics; SAE = serious adverse event; SMBG = self-monitoring blood glucose; WCBP = women of childbearing potential.

- a All measures to be performed at Visit 3 should be done prior to injection of the participant's assigned investigational product (IP) to ensure that appropriate baseline measurements are obtained.
- b Visit 16 is a Phone visit.
- c Visits 20 and ED1 are performed approximately 1 week after the last dose of LY and 1 day after the last dose of degludec. Visit 801 is performed for participants who complete Visit 20. ED1 and ED2 are performed for participants who discontinue study drug but remain in the study.
- d A triplicate, central ECG will be performed in a fasting state at Visits 3, 6, 9, 15, and 17, prior to each PK sample. Patients randomized to insulin degludec treatment will undergo ECG in a fasting state without PK sampling. Only one triplicate ECG is needed for insulin degludec treated patients.
- e Collect 2 PK samples of LY3209590: 1 predose and one approximately 2 hours postdose or as late as possible just prior to departure from the site. ECG will be performed in triplicate prior to the time of each PK sampling at this visit. Note: PK samples are not intended to be collected for participants in the insulin degludec treatment group.
- f Patients will be fitted with Dexcom G6® for CGM monitoring.

Note: Additional visits to ensure correct dosing, titration, and study drug administration can occur anytime during the study if deemed necessary by the investigator and are explicitly allowed and part of the protocol.

2. Introduction

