- The analysis of any postbaseline ALP $\geq 2X$ ULN will contain 4 baseline subsets the same as above for total bilirubin

For the above elevation analysis, maximum baseline and maximum postbaseline will be used. Maximum baseline is defined as the maximum non-missing observation in the baseline period. The maximum postbaseline is defined as the maximum non-missing postbaseline measurements including scheduled, unscheduled and retest measurements.

A listing of patients with any post randomization

- elevation of serum ALT to ≥ 5 -fold ULN on 2 or more consecutive blood tests
- elevated serum TBL to ≥ 2 -fold ULN (except for cases of known Gilbert's syndrome)
- elevation of serum ALP to ≥ 2 -fold ULN on 2 or more consecutive blood tests
- study participant discontinued from treatment due to a hepatic event
- hepatic event considered to be an SAE

will be provided, including demographics, disposition, study drug exposure, AEs, concomitant medications, all the liver measurements (ALT, AST, total bilirubin, ALP and GGT). The time course plot of ALT, AST, ALP, TBL and GGT will also be provided for the patients meeting the above criteria.

5.10.6. *Electrocardiograms*

Electrocardiograms will be collected at specific study visits. For Visit 3, 6, 9, 15 and 17, a triplicate ECG will be collected. The other visits, a single ECG will be collected. The average values will be used in the analysis.

The actual and change from baseline for selected ECG parameters (heart rate and intervals) will be analyzed using the MMRM model. The MMRM model will be used for the analysis during the treatment period and will contain the term for treatment, baseline value, visit, and visit-by-treatment interaction as factors, patient as random effect, and compound symmetric as the variance-covariance structure. The last nonmissing measurements will also be analyzed by the ANCOVA model with treatment and baseline value as covariates.

5.10.7. *Immunogenicity*

The sample to determine antibody against LY3209590 will be collected at protocol-specified visits. Treatment emergent anti-drug antibodies (TEADA) can be subclassified as either treatment induced (baseline antibody level is not detected) or treatment boosted (baseline antibody level is detected):

- treatment induced response: a postbaseline titer ≥ 2 -fold of the minimum required dilution (1:20) if the baseline status is not detected (i.e., titer less than the minimum required dilution)

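### The ECG baseline is fixed by date only, so at Visit 3 it is postdose or a predose/postdose mix for LY3209590 but predose for degludec

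*SAP*

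**What the plan says.** **Baseline rule.** SAP 5.1 takes as baseline "the last non-missing value obtained for each participant prior to or on the date of first study IP dose". Protocol 9.4.1 has the same rule: "the last nonmissing value obtained for each participant prior to or on the date of first study IP dose". Both work on the calendar date and apply unless something else is specified.

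**Visit 3 schedule (protocol 1.3, footnotes).**
- Footnote e gives LY3209590 participants two PK samples at this visit, "1 predose and one approximately 2 hours postdose or as late as possible just prior to departure from the site", and adds that "ECG will be performed in triplicate prior to the time of each PK sampling at this visit".
- Footnote d says of the comparator: "Only one triplicate ECG is needed for insulin degludec treated patients".
- Footnote a says that Visit 3 measures "should be done prior to injection of the participant's assigned investigational product (IP) to ensure that appropriate baseline measurements are obtained".

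**ECG analysis.** SAP 5.10.6 describes the Visit 3 ECG in the singular, as one triplicate, and does not mention the second LY3209590 triplicate. It says "The average values will be used in the analysis" without saying whether the average is taken within a triplicate or over the whole visit. It then plans an MMRM on actual values and changes from baseline, and an ANCOVA on the last value, both with baseline as covariate. It contains no ECG-specific definition of baseline, so the general rule in 5.1 governs.

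**The concern.** A date-based rule is harmless when every first-day measurement comes before the injection. ECG is an exception. Footnote e puts a second triplicate after the injection on the first-dose date, and only in the LY3209590 arm. The rule does not exclude that record, and as the later of the two it is the one a last-value rule selects.

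Change from baseline would then start from a different time of day and a different dosing status in one arm only. Randomization does not remove the difference, because the schedule creates it. It would carry into every later visit in the MMRM and into the ANCOVA, and so into the between-arm 90% intervals and p-values, and the within-arm p-values for change, that SAP 5.1 calls for.

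**Working it through.** The plan states no figure on this point, so there is nothing to reproduce. The check applies the rule to the schedule and then works out what a shifted baseline does.

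**Step 1. Which record becomes baseline?**

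| Reading | LY3209590 | Degludec |
|---|---|---|
| Last value on the first-dose date, averaged within triplicate | postdose triplicate | predose triplicate |
| Average of all ECGs on that date | mean of predose and postdose triplicates | predose triplicate |
| Last triplicate before the first injection | predose triplicate | predose triplicate |

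The degludec column is predose because there is one triplicate and footnote a places it before injection. Neither of the first two rows, which are the readings the SAP allows, gives the same kind of baseline in both arms.

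**Step 2. Effect on the treatment difference.** Let d be the mean postdose minus predose reading on the first day, and β the slope of the later value on baseline. The shift in the LY3209590-minus-degludec difference in change is:
- unadjusted, postdose baseline: -d
- baseline-adjusted, postdose baseline: -β × d
- averaging both triplicates: the LY3209590 baseline moves by d/2 instead of d, so about half of each.

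**Step 3. Illustration.** The documents give neither d nor β. Assume d = 1 to 5 ms for an ECG interval and β = 0.4 to 0.8.
- Unadjusted: -1 to -5 ms.
- Adjusted: from -0.4 × 1 = -0.4 ms to -0.8 × 5 = -4.0 ms.
- Adjusted with averaging: from -0.2 to -2.0 ms.

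**Step 4. Simulation check.** 2,000 runs, 119 per arm (the protocol's number randomized to each treatment), no true treatment effect, assumed SD 10 ms, correlation 0.6 between readings, d = 5 ms.

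| Baseline used for LY3209590 | Mean shift (ms) |
|---|---|
| Postdose, unadjusted | -5.0 |
| Postdose, adjusted | -3.0 |
| Average of both triplicates, adjusted | -1.7 |
| Predose, adjusted | -0.03 (simulation noise) |

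The formulas give -5 and -0.6 × 5 = -3.0 for the first two rows. The averaged case is a little above half of 3.0 because the mean of two triplicates is less noisy, which raises the common slope. The shared variance is 60 in each arm and the baseline variances are 80 and 100, so the slope is 120/180 = 0.67, and 0.67 × 2.5 = 1.7.

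**The case against.** The strongest reply is that the intended baseline is clear. Footnote a says "All measures to be performed at Visit 3 should be done prior to injection", protocol 4.1.1 repeats this, and protocol 8.2.3 has ECGs done before any blood is drawn. SAP 5.10.6 then speaks of one Visit 3 triplicate reduced to an average, and a sensible programmer would use the predose one. The intent does stand. But footnotes a and e are instructions for collecting data, they disagree about Visit 3, and no analysis text carries the predose intent into the baseline rule. Two programmers following the SAP could derive different baselines.

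Four stronger readings are tempting, and the documents do not support them.
- A reader might infer that the LY3209590 baseline is certainly the postdose triplicate. The sentence on average values also allows a predose/postdose mix, which roughly halves the shift.
- A reader might put the heart-rate shift at, say, 1 to 5 bpm. That needs an assumed gap of 2 to 5 bpm and β between 0.5 and 1 (0.5 × 2 = 1; 1 × 5 = 5). None of these values is in the documents, the top end requires β = 1, and averaging is left out.
- A reader might point to meals between the two readings. Footnote d requires the Visit 3 triplicates in the fasting state and 8.2.3 requires supine rest, so under the protocol what remains is mainly time of day and time on site.
- A reader might assume that ECG clock times are available. Protocol 8.5 requires times for PK samples and 6.1.1 for doses; neither document says so for ECGs.

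The objection about importance also stands. ECG is not a listed endpoint in protocol section 3 or SAP section 4, and protocol 9.4.6.5 treats it mainly as safety monitoring with exploratory analysis.

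**Conclusion.** The rule is wrong as written, and the consequence is minor. On either reading of the SAP, the LY3209590 ECG baseline is not like-for-like with degludec and is not the predose baseline that footnote a intends.

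The bias is -d unadjusted and -β × d adjusted, about half that if same-day ECGs are averaged. Its size and direction are unknown, because d and β are not in the documents and the figures in the working are illustrations. The drug-related part of d is probably small: protocol 2.2 reports maximum concentration about 4 days after a single dose in type 2 diabetes. Time of day and time since dosing still differ between the arms.

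The effect is confined to the exploratory ECG safety analyses. The HbA1c comparison and the noninferiority decision are untouched.

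**What to change.** 1. In SAP 5.10.6, state that baseline ECG in both arms is the mean of the last triplicate taken before the first injection. Identify it by ECG time if that is captured; otherwise, for LY3209590, by its pairing with the predose PK sample. Degludec has a single Visit 3 triplicate, so no choice arises there.
2. State in the same place that the average is taken within a triplicate, and that the LY3209590 postdose triplicate is a separate postbaseline time point that does not enter the baseline used for the between-arm comparison.
3. Reconcile footnote e with footnote a and protocol 8.2.3, since a triplicate taken after the injection and after the predose PK sample fits neither as worded.

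The cost is a sentence or two in the SAP and a clarification in the protocol. No data collection, sample size or primary analysis changes.
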